**Table D3-2. Cortisol change detectable with 80% power for varying values of  $r$ .**

$r$	Effect Size	Difference Detectable with $\sigma = 2.2$
0.25	$0.77\sigma$	1.7
0.50	$0.63\sigma$	1.4
0.75	$0.44\sigma$	1.0
0.90	$0.28\sigma$	0.6

Preliminary data in a small group of OSA+ PCOS subjects indicate that the mean cortisol level was  $10.2 \pm 2.2$  (Mean  $\pm$  SD). Using the SD from the preliminary data, for example, this study would be powered to detect a difference of  $0.63 \times 2.2 = 1.4$  if the correlation is 0.50 (see **Table 2**).

Cortisol levels at time T2 will be compared to the levels at T1 using a paired  $t$  test. Additionally, the association between the changes ( $T_2 - T_1$ ) in cortisol and in total AHI with treatment will be assessed using Pearson correlation coefficients or Spearman rank correlation coefficients, as appropriate.

**D4. Potential pitfalls and plans for their resolution**

re: Specific Aim 1. In studies conducted under Specific Aim 1, subjects will be recruited to participate in a wide variety of procedures over a number of weeks. Recruitment and retention may pose challenges, however we have longstanding experience with studies of this nature and our recruitment procedures have been successful to date; our retention rates in similar studies has been over 90%. Subjects are contacted on a regular basis by our study coordinator. Subjects also receive monetary compensation for participation in the protocols. We have successfully recruited subjects in the past through cooperation with other physicians who care for patients with PCOS and we plan to do so again in the event that recruitment goals are lagging.

re: Specific Aim 2. Studies in this Aim are anticipated to flow smoothly. Potential problems include drop-outs related to intolerance/untoward effects of study medication and lack of compliance. It is anticipated that additional subjects may need to be recruited to replace the drop-outs. Another potential pitfall is that the degree of testosterone suppression expected after depot-leuprolide administration may be insufficient (i.e., testosterone levels may remain above the normal female range). If this proves to be the case, we will use testosterone concentration as a covariate in our analyses related to metabolic changes pre- and post-leuprolide. Likewise, even though micronized estrogen and progesterone are optimized for oral absorption, if serum levels of estrogen and progesterone achieved are below the expected range observed in normal women, we will use these hormone concentrations as covariates in our statistical analyses. Although transdermal (patch or cream preparations) were an alternative to oral hormone therapy, the assessment of compliance with their use would have posed challenges. Pill counts, patient contact on a regular basis, and measurement of hormone levels in blood will be used to ensure and document use of study medication.

re: Specific Aim 3. This protocol requires high levels of commitment from study subjects who must use CPAP on a regular basis for the duration of the study. Compliance with CPAP use is automatically recorded and powering on the device can be differentiated from patient use via sensors incorporated into the CPAP mask. Thus, we will have device-generated compliance records.

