**At 15:50, a GnRH agonist test will be performed, as depicted in FIGURE D2-3 below.**

At 15:50, a 15cc blood sample for LH, FSH, estradiol, estrone, total and free testosterone, progesterone, 17-hydroxyprogesterone, and androstenedione will be obtained. At 15:59, a 5 cc blood sample will be taken for LH and FSH. At 16:00, leuprolide acetate 10 µg/kg will be given as a single subcutaneous injection. At 16:30, 17:00 and 20:00, 5 cc samples will be obtained for LH and FSH. A 15 cc sample will be obtained for estradiol, estrone, total and free testosterone, progesterone, 17-hydroxyprogesterone, and androstenedione after 16, 20, 24 hours GnRHa administration, i.e. at 8:00, 12:00 and 16:00.

As depicted in Figure D1-1, it is at this point that subjects will have completed the Screening and Specific Aim 1 Procedures. Details of procedures for subjects randomized into Specific Aim 2 or Specific Aim 3 are provided below.

### D3. Detail of methods pertaining to Specific Aims 2 and 3

The PCOS women with OSA studied in Aim 1 plus additionally enrolled PCOS women with OSA (for a total of 60 subjects) will be randomized in a ratio of 2:1 to participate in Aim 2 (n=40) or Aim 3 (n=20). Block randomization will be performed using computer-generated random numbers. The primary outcomes measure for Aim 2 is the AHI difference pre- and post-interventions, as detail in Section D3; the primary outcomes measure for Aim 3 is the change in 24 hr cortisol concentration pre- vs post-CPAP

Subjects randomized to Specific Aim 2 will have suppression of endogenous LH secretion, and thus ovarian sex-steroid production, by administration of a single intramuscular dose (11.25 mg) of the GnRH agonist depot leuprolide. Leuprolide is a synthetic nonapeptide analog of naturally occurring gonadotropin-releasing hormone (GnRH). The analog possesses greater potency than the natural hormone. When the depot form of leuprolide is administered at a dose of 11.25 mg, there is prolonged (3 month) suppression of pituitary gonadotropin levels and ovarian steroid levels as documented in the literature (115) and exemplified in Preliminary Studies. Six-weeks after administration, subjects will return to the GCRC for repeated evaluation, identical to that conducted at Baseline under Specific Aim 1.

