### D3. Statistical Considerations

#### re: Specific Aim 1

With 20 subjects per group and assuming a two-sided alpha level of 0.05, there would be approximately 80% power to detect a 0.89 SD difference in progesterone or estrogen levels between PCOS women without and PCOS women with OSA. These values are derived from data obtained in a group of 10 PCOS women without OSA. Using the SD from the preliminary data, this study would be powered to detect a 42% difference in hormone levels between groups.

46 subjects will need to be enrolled for this Aim in order to ensure a sample size of 20 in the group of PCOS women without OSA; this figure of 46 subjects is based on an estimated 55% prevalence of OSA among PCOS women as shown in Preliminary Studies.

Progesterone and estrogen levels will be compared between the two groups using a two sample *t* test. A log transformation of the data will be performed if there is evidence of non-normality. Statistical correction will be made for multiple comparisons between groups.

#### re: Specific Aims 2 and 3

The PCOS women with OSA studied in Aim 1 plus additionally enrolled PCOS women with OSA (for a total of 60 subjects) will be randomized in a ratio of 2:1 to participate in Aim 2 (n=40) or Aim 3 (n=20). Block randomization will be performed using computer-generated random numbers.

#### • Specific Aim 2

For this Aim, there are three time points of interest: baseline (T1), six weeks after administration of depot leuprolide (T2), and at the end of study after receiving six weeks of either estrogen or progesterone

(T3). Treatment assignment to either estrogen (n=20) or progesterone (n=20) will be randomized using computer-generated random numbers.

If the variance in AHI is denoted by  $\sigma^2$  and the correlation between pre- and post-treatment AHI by  $r$ , then the variance of the change in AHI is given by  $2\sigma^2(1-r)$ . With 20 subjects per group and assuming a two-sided alpha level of 0.05, the **Table D3-1** below lists the difference in AHI change detectable between the two treatment groups with 80% power for varying values of  $r$ .

**Table D3-1. Difference in AHI change detectable between the two treatment groups with 80% power for varying values of  $r$ .**

$r$	Effect Size	Difference Detectable with $\sigma = 8$
0.25	$1.08\sigma$	8.6
0.50	$0.89\sigma$	7.1
0.75	$0.63\sigma$	5.0
0.90	$0.40\sigma$	3.2

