Polysomnography results in a group of 17 PCOS women with OSA (defined by a total AHI  $\geq 10$ ) indicate that the mean AHI was  $18.4 \pm 8$  (Mean  $\pm$  SD). Using the SD from these preliminary data, for example, the present study would be powered to detect a difference of  $0.63 \times 8 = 5.04$  if the correlation is 0.75 (see **Table D3-1**). This would be equivalent to a mean change in AHI of 9.2 (a 50% decrease from baseline assuming a baseline level of 18.4) in the progesterone treated group versus a mean change of 4.2 (23% decrease from baseline assuming a baseline level of 18.4) in the estrogen treated group. The change in AHI ( $T_3 - T_1$ ) will be compared between the two groups using a two sample  $t$  test. This would amount to performing repeated measures analysis of variance on AHI and testing for group (progesterone vs. estrogen), time (pre- vs. post-treatment), and group by time interaction effects. The analysis will be performed both ways. Additionally, testosterone, estrogen, and progesterone levels at time T2 will be compared to the levels at T1 using a paired  $t$  test.

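### Aim 2 tests the T3−T1 change in AHI and replaces drop-outs, so losses after the estrogen/progesterone randomisation can bias the arm comparison

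*Combined protocol and SAP*

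**What the plan says.** The first of the two sections numbered D3 (detail of methods for Aims 2 and 3) defines the endpoint: "The primary outcomes measure for Aim 2 is the AHI difference pre- and post-interventions". It places the estrogen/progesterone randomisation after the midpoint assessment, six weeks after depot leuprolide.

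D3, Statistical Considerations, names three time points: baseline (T1), six weeks after leuprolide (T2), and after six weeks of hormone (T3). The change T3−T1 "will be compared between the two groups using a two sample" t test. The plan describes a pre/post repeated measures analysis of variance as amounting to the same thing, and adds: "The analysis will be performed both ways". On allocation: "Treatment assignment to either estrogen (n=20) or progesterone (n=20) will be randomized using" computer-generated random numbers. Sizing is stated as "With 20 subjects per group and assuming a two-sided alpha level of 0.05".

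D4, for Aim 2: "Potential problems include drop-outs related to intolerance/untoward effects of study medication and lack of compliance". The next sentence gives the remedy: "It is anticipated that additional subjects may need to be recruited to replace the drop-outs". D4 also plans pill counts and blood hormone levels, and would use hormone levels as covariates if they fall below the expected range.

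The documents do not define an analysis set, give a rule for a missing T3 AHI, provide for a T3 polysomnogram in women who stop capsules, or say how a replacement is allocated.

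**The concern.** A T3−T1 change exists only for a woman with a T3 polysomnogram, and the repeated measures version offered alongside uses the same two occasions. With replacement as the only stated handling of drop-out, the t test compares two sets of women who reached T3. Women who were assigned estrogen or progesterone and then left contribute nothing to it.

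The reasons D4 names can depend on the assigned drug. The risk section lists nausea for estrogen only and depression for progesterone only; headache, breast tenderness and bloating are common to both. If more women leave one arm, and those who leave would have responded differently, the two groups compared are no longer those formed by randomisation. Replacement restores the count of 20 but not that comparability. This is the only randomised drug contrast in the project.

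**Working it through.** **1. The plan's own figure.** Inputs from D3, Statistical Considerations: 20 per arm, two-sided alpha 0.05, 80% power, SD of AHI 8, correlation 0.75. The SD of change is 8 × √(2 × (1 − 0.75)) = 5.66. The detectable difference is (1.960 + 0.842) × √(2/20) × 5.66 = 5.01 events/hr, or 0.626σ. Table D3-1 gives 0.63σ and 5.0, and the text uses 0.63 × 8 = 5.04. The figure reproduces (normal approximation). It contains no allowance for drop-out, so 20 means 20 women with a T3 value.

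**2. What replacement achieves.** For a difference of 5.04, power is 80% with 20 per arm, 76% with 18 and 71% with 16. Replacement protects power.

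**3. Which losses matter.**
- *Between T1 and T2 (leuprolide phase):* no hormone has been assigned. Losing or replacing these women changes who is studied, but cannot make the two arms differ systematically.
- *Between T2 and T3 (hormone phase):* the arm is assigned. Losses here can depend on it. D4 does not separate the two phases.

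**4. Size of the bias.** In one arm, let q be the drop-out share and g the amount by which drop-outs' mean AHI change is worse than completers'.

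- Mean of all randomised = (1 − q) × completer mean + q × drop-out mean
- Completer mean − mean of all randomised = q × g
- Bias in the arm difference = q₁g₁ − q₂g₂, which is (q₁ − q₂) × g when the gap is the same in both arms

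The documents give no Aim 2 rate by arm, so the rates are assumptions. For the gap I use the two mean changes in the plan's worked example, 4.2 and 9.2 events/hr. The standard error of the arm difference is 5.66 × √(2/20) = 1.79.

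| Drop-out rates | Gap | Bias (events/hr) | Share of 5.04 | Two-sided type I error |
|---|---|---|---|---|
| 10% and 10% | either | 0 | 0% | 5% |
| 10% and 20% | 4.2 | 0.10 × 4.2 = 0.42 | 8% | about 6% |
| 10% and 20% | 9.2 | 0.10 × 9.2 = 0.92 | 18% | about 8% |

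In an arm of 20, rates of 10% and 20% are two women and four women. The arm that loses more looks better than it should.

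**5. What analysing all randomised women does to the difference.** Suppose drop-outs have zero change and the plan's 9.2 and 4.2 apply to completers. With 10% loss in each arm the difference is 0.9 × 9.2 − 0.9 × 4.2 = 4.5, with power 71% at 20 per arm and 25 per arm needed for 80%. With 20% in each arm it is 0.8 × 9.2 − 0.8 × 4.2 = 4.0, with power 61% and 32 per arm. Here the gaps differ by arm (9.2 and 4.2), so the difference shrinks even though the rates are equal.

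**6. Does a mixed model repair it?** T1 and T2 both precede the hormone randomisation. A woman with no T3 therefore supplies no on-hormone AHI. A model using T1, T2 and T3 corrects for loss that T1 and T2 AHI explain, and for no other loss. In a simulation with 20% loss in one arm only, unrelated to T1 or T2, gap 9.2 and r = 0.75, the bias was 1.84 for the completer t test and 1.85 for the likelihood-type estimate.

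**The case against.** The strongest reply is that D4 is a recruitment remark in a pitfalls section, not an analysis rule. Nothing says that drop-outs' data are discarded or that losses will go unreported. The paired T2-versus-T1 comparison of hormone levels needs no T3, so early data do have a use. That is correct: completers-only is an inference from the T3−T1 test, not a term in the plan. But with no missing-T3 rule, neither of the two analyses offered can use a woman without a T3 value, so the inference stands for the primary comparison.

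Other points on that side also hold:
- **Expectation of drop-out.** A reader might infer that the plan expects drop-out. D4 calls it a potential problem, says replacements may be needed, and anticipates that the studies will flow smoothly. Retention above 90% is cited under Aim 1 for similar studies.
- **Evidence for differential loss.** It is limited. Most listed side effects are shared and treatment is double-blind. Unequal loss is possible, not shown.
- **Non-compliance.** Pill counts and the hormone covariates suggest that women with low exposure stay in the analysis. They do not supply a missing AHI.
- **Larger figures.** Putting a 20% loss wholly in one arm with a 9.2 gap gives 1.84 events/hr, 37% of 5.04. The documents do not support treating that as the likely size: it assumes no loss in the other arm, and in the estrogen arm, where the assumed change is 4.2, a 9.2 gap would mean that drop-outs worsen.

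**Conclusion.** The concern holds in a limited form. As written, the Aim 2 primary comparison uses women who reached T3, topped up by replacement, and losses after the post-T2 randomisation can bias it. Assuming drop-out of 10% in one arm and 20% in the other, and an equal gap of 4.2 to 9.2 events/hr, the bias is about 0.4 to 0.9 events/hr. The actual size cannot be taken from the documents and may be zero.

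Three stronger readings are not supported. The sample size is not wrong, since Table D3-1 reproduces. Replacing women lost in the leuprolide phase does not bias the arm contrast. A mixed model that merely keeps drop-outs' T1 and T2 values is not a sufficient cure. The change is worth making because the threatened contrast is the randomised one and the remedy is cheap.

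**What to change.** Amend D3 (Statistical Considerations) and D4 for Aim 2:

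1. Restrict replacement to women lost before the post-T2 randomisation. Give any woman added later the next number in the schedule, in addition to the drop-out and not instead of her.
2. Invite women who stop capsules to the T3 polysomnogram already scheduled. This is the essential step.
3. Make the primary analysis all women randomised after T2, in their assigned arm, with T1 and T2 AHI as baseline information (mixed model or ANCOVA).
4. Report drop-out by arm, separately for the leuprolide and hormone phases.
5. As sensitivity analyses, give the completer t test and an analysis that assumes worse outcomes in women missing T3.

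The cost is plan wording, somewhat more analysis work and slightly unequal arms. No new procedure is needed. Keeping 20 evaluable women per arm means randomising 20/0.9 = 22.2, so 23 per arm, at an assumed 10% missing T3, or 20/0.8 = 25 at 20%. The estimated difference may be somewhat smaller than among completers, as step 5 of the working shows, and power should be judged with that in mind.

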**Specific Aim 2. To determine if OSA improves in women with PCOS treated with estrogen or progesterone.** For these studies, we will enroll women with PCOS who have OSA. Subjects will have a detailed baseline metabolic and metabolomic profile together with a baseline polysomnogram. Subjects will then receive a single dose of depot-leuprolide in order to suppress ovarian production of estrogen, progestin, and androgen over a period of 3 months. Six weeks after administration of depot-leuprolide, subjects will have repeated assessment of metabolic, metabolomic, and sleep measures to determine if these outcomes are altered by the combined suppression of ovarian sex steroids. Subsequently, subjects will be randomized in a double-blind placebo controlled fashion to one of two treatment arms for a period of six weeks. Treatment arms are: estrogen plus placebo or progesterone plus placebo. At the end of this second six weeks, subjects will have metabolic, metabolomic, and sleep measures repeated. Primary outcome measures will be compared both within and between treatment arms.

**Specific Aim 3. To determine if metabolic disturbances present in PCOS women with OSA are ameliorated by the treatment of OSA with continuous positive airway pressure (CPAP).** The presence of OSA in women with PCOS has a significant negative effect upon metabolic measures. In particular, the presence of OSA in PCOS is associated with hyperinsulinemia, elevations in plasma glucose, and lipid abnormalities that include higher levels of triglycerides and LDL-cholesterol. OSA in PCOS is also associated with hypercortisolemia that persists throughout both day and night. Results of our preliminary studies indicate that CPAP treatment of OSA results in attenuation of cortisol levels not only during sleep, but throughout waking hours as well. This aim will serve to test the hypothesis that correction of OSA in PCOS will lead to improved metabolic function which can be attributed, at least in part, to a reduction in circulating levels of cortisol.

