After this midpoint assessment, subjects will again enter into a randomized phase of the protocol. Subjects will be assigned to receive one of two treatment regimens in a randomized, double-blind, placebo controlled fashion, for a period of 6 weeks. Subjects will receive daily oral doses of either **2 mg micronized estradiol (Estrace®) plus placebo –OR– 200 mg micronized progesterone (Prometrium®) plus placebo.**

Rationale for preparation and dose of estrogen and progesterone. Natural estradiol is poorly absorbed in its native form and undergoes rapid metabolism in a first-pass effect through the liver. Thus, micronization (micronized estradiol) or acetylation (ethinyl estradiol) is required to achieve adequate blood hormone levels. Micronized estradiol is extremely well-absorbed and much of the compound is metabolized to estrone sulfate (65%) and estrone (15%). This “pool” of estrone and estrone sulfate then serves as the source of regenerated estradiol. At a dose of 2 mg per day, the steady-state levels of estradiol and estrone are typically 220 pmol/L and 68 pmol/L, respectively (116) and most closely recapitulate those seen in normal women in the midfollicular phase of the menstrual cycle (110). Because ethinyl estradiol is poorly converted to estrone, it will not be selected for use in these protocols. Micronized progesterone at a dose of 200 mg per day has been reported to result in attainment of serum progesterone concentrations typically seen in the late follicular/early luteal phase of the cycle (data provided by manufacturer).

Subjects randomized to Specific Aim 3 will be treated with nasal CPAP for a period of 6 weeks. Compliance will be documented based upon results provided by a microchip sensor that detects not only if the unit is powered on, but also if the mask is being worn by the subject. These data cannot be altered by the individual and there is no access to this microsensor by the user. The subjects who have OSA will undergo one night of CPAP titration study at the end of the baseline assessment. After 6 wks of home CPAP, the experimental study outline above will be repeated with CPAP use at night. Subjects whose average nightly CPAP use is > 5 hr will be considered compliant.

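### The Aim 2 contingency in D4 would adjust for achieved estrogen and progesterone levels without exempting the randomised AHI comparison or saying which result governs

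*Combined protocol and SAP*

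**What the plan says.** D3 (Detail of methods pertaining to Specific Aims 2 and 3) fixes the endpoint: "The primary outcomes measure for Aim 2 is the AHI difference pre- and post-interventions". It also fixes the order of events. Depot leuprolide comes first and the midpoint evaluation follows six weeks later. Then "After this midpoint assessment, subjects will again enter into a randomized phase of the protocol", in which each woman receives estradiol or progesterone for six weeks.

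D3 (Statistical Considerations) defines T3 as the visit "at the end of study after receiving six weeks of either estrogen or progesterone". It compares the AHI change (T3 - T1) between arms by a two-sample t test and by repeated measures analysis of variance with group, time and group-by-time terms. Neither analysis has a hormone covariate.

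D4 then gives two contingency rules for Aim 2. If testosterone suppression is insufficient, "we will use testosterone concentration as a covariate in our analyses related to metabolic changes pre- and post-leuprolide". The next sentence opens with *Likewise* and says that "if serum levels of estrogen and progesterone achieved are below the expected range observed in normal women, we will use these hormone concentrations as covariates". The first rule names the analyses it covers. The second does not: it speaks only of the statistical analyses in general.

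**The concern.** The levels achieved on study drug are measured after the estrogen/progesterone randomisation. They are set largely by the assigned drug, on a background of suppressed ovarian production. They are also the proposed mechanism: Section A hypothesises that circulating progesterone and estrogen levels are determinants of sleep apnea in these women. An arm coefficient that holds these levels constant asks what assignment does apart from the levels it produces, which is not what the randomised comparison is designed to answer.

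If the rule were applied to the AHI comparison, the adjusted coefficient could move toward zero, move away from zero or change sign, and it would usually lose precision. The plan would then hold two arm effects for its primary endpoint with no statement of which one counts, and the choice would arise after hormone levels were known.

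**Working it through.** **Inputs from the plan** (D3, Statistical Considerations): 20 women per arm; two-sided alpha 0.05; SD of AHI 8; pre/post correlation 0.75; falls of 9.2 (progesterone) and 4.2 (estrogen). Taking progesterone minus estrogen, the difference in change is -9.2 - (-4.2) = -5.0.

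**1. The plan's own figure.**
- SD of change = 8 × √(2 × (1 - 0.75)) = 5.66.
- Detectable difference = (1.960 + 0.842) × √(2/20) × 5.66 = 5.01. The plan gives 0.63 × 8 = 5.04, so it reproduces.
- Unadjusted SE = 5.66 × √(2/20) = 1.79.
- Power for 5.0 is 0.78 by the noncentral t. For 5.04 it is 0.80 by the normal approximation.

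**2. Expected coefficient with both levels entered.** Assumptions, none of them in the documents:
- the rule fires;
- each arm is 2 within-arm SDs higher on its own hormone;
- a share mP of progesterone's fall and mE of estrogen's acts through serum level, and the rest is direct;
- level and AHI change share no other cause.

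Expected adjusted coefficient = -(1 - mP) × 9.2 + (1 - mE) × 4.2.

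Results by simulation (20 per arm, SD of change held at 5.66, least squares):

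| mP, mE | Arithmetic | Adjusted coefficient | SE | Power |
|---|---|---|---|---|
| 1, 1 | 0 + 0 | 0 | 1.4 | 0.05 |
| 0.5, 0.5 | -4.6 + 2.1 | -2.5 | 2.9 | about 0.15 |
| 0, 0 | -9.2 + 4.2 | -5.0 | 3.2 | 0.33 |

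Unequal shares give the extremes. With only estrogen's effect through levels the coefficient is -9.2 + 0 = -9.2. With only progesterone's it is 0 + 4.2 = +4.2, a change of sign.

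**3. Why precision falls even when nothing acts through levels.** Each level is strongly related to arm. With 38 within-arm degrees of freedom, SE ≈ 5.66 × √(2/20 + (2² + 2²)/38) = 5.66 × 0.557 = 3.15, against a simulated 3.2. At separations of 1, 2, 3 and 4 SD the simulated SE is 2.3, 3.2, 4.4 and 5.6, and power is 0.58, 0.33, 0.20 and 0.14.

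**4. Shared cause of level and AHI change.** Suppose nothing acts through levels, but within arms progesterone level and AHI change correlate at ±0.3 (assumed) through a common cause. The slope is 0.3 × 5.66 = 1.70 per SD. Over 2 SD this shifts the coefficient by 3.4, giving -5.0 - 3.4 = -8.4 or -5.0 + 3.4 = -1.6. The estimate is therefore unchanged in expectation only if both conditions hold: no effect through levels and no shared cause.

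**5. A scenario closer to the trigger.** The rule fires only when levels are low, so the plan's full falls may be optimistic. If both falls are halved (4.6 and 2.1), the unadjusted difference is -2.5 with power 0.28. At 2 SD the adjusted coefficients, in the order of the table, are about 0, -1.25 and -2.5, the last with power 0.12.

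**The case against.** The strongest reply is that the rule was never meant for AHI. The testosterone rule is limited to metabolic changes, and *Likewise* can carry that limit forward. One might answer that the limit cannot apply because the study hormones start only after T2, but the documents do not support that answer. Section A (Specific Aim 2) repeats metabolic and metabolomic measures at the end of the second six weeks, and the section relating this project to the others plans to look for metabolic changes with hormonal modulation. A metabolic-only reading is therefore open. It is still not stated, and the contrast with the explicitly limited testosterone sentence leaves the scope undefined.

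Second, D3 specifies the unadjusted AHI comparison unconditionally and D4 withdraws nothing. This stands. A reader might infer that the plan replaces its primary analysis with a hormone-adjusted one, but nothing in the text says so. What is missing is a rule of precedence.

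Third, Section A says "Primary outcome measures will be compared both within and between treatment arms", so achieved levels could be used within arms, where the difficulty does not arise. That is fair, but D4 does not confine the rule to that use.

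Fourth, the sizes rest on assumed inputs. This also stands. In particular, the sign reversal needs progesterone to act wholly through serum level and estrogen not at all. The documents do not support that split, since the hypothesis gives a role to both circulating levels.

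**Conclusion.** The point holds as a defect of scope and precedence in D4. It is not an error in the test that D3 specifies. Harm requires that levels fall short, that the rule is read to include AHI and that the adjusted result is given weight. The documents establish none of these, and they rule out neither the second nor the third.

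If the rule is applied to AHI, the adjusted arm coefficient does not in general estimate the effect of assignment. That conclusion follows from the timing and role of the hormone levels and needs no particular numbers. The sizes (about 0, -2.5 or -5.0 in place of -5.0, with power of 0.05, about 0.15 or 0.33 in place of 0.78) are illustrations under the assumed 2 SD separation, the assumed shares and no shared cause. It would be wrong to read the no-mediation case as showing that adjustment costs only precision, because a shared cause would bias it as well.

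**What to change.** In D3 (Statistical Considerations, Specific Aim 2) and in D4, state that the as-randomised comparison of AHI change (T3 - T1), with no post-randomisation covariates, is the primary Aim 2 analysis whatever hormone levels are achieved. In D4, confine achieved estrogen and progesterone levels to a separately labelled secondary exposure-response analysis within each arm. This keeps the investigators' interest in exposure and removes any doubt about which arm effect is reported as primary. It costs wording only: no new data, visits or subjects.
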